1. INTRODUCTION

Wound healing is a complex and dynamic biological process consisting of a series of organised stages, including coagulation, inflammation, matrix deposition, angiogenesis, proliferation, cell remodelling and wound contraction (1, 2). To complete each stage of the process, complex interactions must take place between several biological factors, such as growth factors and proteases, matrix components and various types of cell, such as platelets, macrophages, fibroblasts and endothelial cells (3). The interaction between these processes as a whole results in restored tissue integrity and functional healing (4). Although it is generally acknowledged that most acute wounds can heal following the ordered sequence of events described above within 2-4 weeks, sometimes, due to changes occurring during the natural healing process, a pathological scar (either a hypertrophic scar or a keloid scar) can form. In addition, the healing process may be blocked at various stages of the regenerative process, which prevents the affected area from healing, giving rise to the development of chronic skin wounds (ulcers¹). Many factors can contribute to the occurrence of these events, some of which are already known, whereas others such as diabetes, venous or arterial disease, infections, metabolic disorders and advanced age are still being investigated.

Therefore, the proper management and treatment of wounds after surgery, trauma or a pathological process plays an important role in the healing process, not only to prevent the onset of infections or other complications but also to accelerate the wound healing process and limit scarring as much as possible.

Although much work has already been done to fully understand the processes governing this extremely important biological function, many aspects remain unclear. Although it is true that technological progress has led to the creation of increasingly sophisticated treatments, there is also a need to find new methods that can further improve the healing process, irrespective of the cause of the skin lesion, reducing the pain and discomfort associated with the medication itself and potentially shortening the healing time, thereby reducing the associated costs.

The purpose of this study is to evaluate the efficacy of the EmoLED device in promoting the healing of skin ulcers. As it is an innovative device, data relating to its use in humans has not yet been reported in the literature. A first pilot study investigated the use of the above-mentioned device on skin sampling areas in patients treated by the Centro Grandi Ustioni [Severe Burn Centre] of the AOUP (Azienda Ospedaliero-Universitaria Pisana [Pisana University Hospital]). This study demonstrated the clinical safety of the device as well as its non-inferiority compared to other types of advanced treatment.

This study will consider skin ulcers of various aetiologies. Depending on the size of the wound or the presence of multiple wounds, the EmoLED device will be used to treat either the whole wound or half of the wound.

How the treatment will be applied will be explained in detail below. However, in short, treatment with EmoLED consists of irradiating the wound (or part of the wound) for 60 seconds with the light emitted by the device. This treatment is used as an adjuvant to standard therapy.

This treatment does not interfere with other systemic therapies that may be being administered, nor does it involve any additional risk compared to SOC. The potential benefit is reduced healing time, with the consequent indirect benefits that this entails.

1.1 Operating principle of the EmoLED medical device in supporting wound healing

The EmoLED device is a medical device designed to support wound healing, whose operation is based on LEDs that emit blue light. It has not yet attained CE marking as its certification process is pending.

Blue light was chosen based on Anderson and Parrish's theory of selective photothermolysis, according to which selective heating of a target chromophore is achieved when the source wavelength – our LEDs – is preferentially absorbed by the chromophore – Protoporphyrin IX of the haem group and Cytochrome c group.

¹ According to Welfare reports, 1% of adults in Italy suffer from leg ulcers. This percentage increases to 3.6% in adults over the age of 65 years.

Regarding the use of light in medicine, the scientific literature is abound with data and evidence on its use, both for the treatment of acne (5) and psoriasis (6) and on its efficacy in accelerating the healing process in animal models of induced wounds (7), (12).

When considering the skin chromophore absorption coefficients within the range of the visible spectrum, it is observed that haemoglobin reaches its maximum absorption peak within the blue range: at around 410 nm for oxyhaemoglobin (HbO_2) and around 430 nm for deoxyhaemoglobin (deoxy-Hb). This particular property is exploited to induce a localised temperature increase in order to stimulate a rapid coagulation effect. The use of the selected wavelength range also ensures that the thermal effect is focussed entirely on the areas where haemoglobin is present, thereby limiting the effect on the healthy tissues surrounding the wound through reduced absorption by the other skin chromophores (11).

A review of the relevant literature shows that vanilloid receptors, which are sensitive to different temperature ranges and are expressed by various cell types present in the treated tissues (8), (9), (10), may be activated by the thermal action of the EmoLED device on haemoglobin. Of the various receptors that may be involved, it is worth mentioning the TRPV1, TRPV3 and TRPM7 channel receptors, which are co-expressed and mutually regulated. The activation of these receptors by thermal stimulation triggers a signal transduction pathway in the cells. This pathway is involved in phenomena such as mast cell degranulation as well as the release of pro-inflammatory mediators and the production of collagen, ultimately accelerating the overall healing mechanism. Another pathway through which the EmoLED device can act is the mitochondrial electron transport chain. More precisely, EmoLED can act on the last two complexes containing Cytochrome c, which is also sensitive to the visible light emitted by the device. The resulting effect is an enhancement of this process as well as an increase in ATP production related to the development of an electron transport chain-dependent proton gradient. Increased ATP production results in an increase in the amount of energy available to cells, which can enhance their metabolic activity. This process is necessary for wound repair because healing involves the simultaneous activation of different cell types and additional energy consumption by the body.

The device has been manufactured and programmed to provide a power density of approximately 5 J/cm² within an acceptable treatment time both for doctors and patients, corresponding to 60 seconds for every 5 cm x 5 cm area to be treated.

Treatment duration was also chosen based on the data reported in the literature on thermal injury. The temperature generated by the treatment on the treated area ranges from 45°C to 50°C, which is optimal for stimulating the induction of the desired reversible and physiological phenomena.

A table detailing the temperature-induced physiological phenomena is provided on page 78 of (13) and attached hereto:

Table 3.6. Thermal effects of laser radiation

| Temperature | Biological effect |
|-------------|---|
| 37°C | Normal |
| 45°C | Hyperthermia |
| 50°C | Reduction in enzyme activity, Cell immobility |
| 60°C | Denaturation of proteins and collagen, Coagulation |
| 80°C | Permeabilization of membranes |
| 100°C | Vaporization, |
| | Thermal decomposition (ablation) |
| > 150°C | Carbonization |
| > 300°C | Melting |

The same source shows a curve demonstrating a link between the duration of thermal stimulation and the degree of reversibility of the process induced by thermal stimulation.

[figure not shown]

Fig. 3.21. Critical temperatures for the occurrence of cell necrosis. Data according to Henriques (1947) and Eichler and Seiler (1991)

This finding concerning the temperature-induced physiological effects constituted the foundation for the definition of the treatment parameters.

In addition to the studies on thermal influence, the choice of treatment duration is based on a finite element model (14) which correlates optical power to treatment duration and the final temperature induced by the treatment with the device. The initial model led to the identification of the optimal working conditions. These were subsequently tested in an animal model study.

As reported in the article, the animal study evaluated treatment efficacy adjusted to the standard represented by an abrasion produced on the back of the animal using a mechanical abrasion instrument. No thermal injury was observed in the tissue surrounding the wound and it was confirmed that a single treatment was sufficient to trigger and accelerate the wound healing process.

The above-mentioned mechanisms are in line with the findings directly observed during a preclinical study of an animal model as part of the LighTPatH project within the 2012 BiophotonicsPlus call, which used a fibre optic version of the EmoLED device to treat abrasions produced on the back of male albino CD-1 mice.

PRE-CLINICAL ANIMAL MODEL STUDY PROTOCOL

Mice were anaesthetised with ketamine (80-100 mg/kg, IP) and xylazine (10 mg/kg) intraperitoneally and placed on a warming pad heated to 37.5°C to prevent further anaesthesia-induced stress. Their backs were shaved using an electric razor. Each animal received two wounds, one rostral and one caudal, inflicted by an abrasor. The two wounds, measuring 1 cm in diameter, were marked out and delimited. One of the wounds was treated with the EmoLED device. Subsequently, both of them were treated with Streptosil (neomycin) (topical preparation) to prevent the onset of infections.

The treatment with the EmoLED device lasted 30 seconds in all cases (the EmoLED device we intend to test in humans can treat round areas up to 2 cm in diameter; for larger wounds, a 30-second treatment will have to be repeated for each sub-area until the whole area is treated).

After the treatment, the animals were housed in individual thermostatic cages until they awoke from anaesthesia. During the healing process, prior to sacrificing them, the animals were housed in individual cages under controlled temperature and light conditions (21-24°C and 12/12 hours of dark and light cycles) and supplied with standard water and rodent pellets ad libitum.

PRECLINICAL ANIMAL MODEL STUDY OBSERVATIONS

The observations reported below were extrapolated from tests performed on biopsies taken at specific time points. After the treatment, each animal was observed over a given follow-up period before being sacrificed. The areas to be studied were collected and embedded in a compound suitable for cryosectioning (frozen section). They were then used both for histological and immunohistochemical analyses.

A large number of observations were collected. They are reported below by making reference to the observed phenomenon.

Inflammatory infiltrate: based on the data obtained 0, 1, 3, 6, 9, 12, 18 and 24 hours after inflicting the wound, it is noted that within the first few hours the amount of inflammatory infiltrate in the areas treated with the EmoLED device is higher compared to the untreated wound. The difference becomes smaller between 9 and 18 hours until, after 24 hours, the situation is reversed and the amount of inflammatory infiltrate in the untreated wound is higher than that in the treated wound.

Mast cells and Mast Cell Degranulation Index: although no particular differences in the number of mast cells were found between the treated and untreated samples, this was not the case when mast cell activation was studied: in fact, potent degranulation was observed in the treated sample at 3 hours, which was not seen in the wound not treated with the EmoLED device.

Macrophage populations: observations made 0, 3, 6, 9, 18 and 24 hours after inflicting the wound on the populations of M1 macrophages (proinflammatory) and M2 macrophages (pro-healing) show that the anti-inflammatory phase begins 6 hours after inflicting the wound in animals treated with the EmoLED device, whereas it is necessary to wait 18 hours for the inflammatory phase to end with the standard treatment. Moreover, after 18 and 24 hours, both the M1 and M2 populations are comparable in the treated and untreated samples, demonstrating that treatment with the EmoLED device does not induce responses other than normal physiological reactions.

Based on these studies, it can be concluded that the EmoLED device exerts its effect within the first few hours after wound infliction (and therefore within the first few hours after treatment). Our hypothesis is that treatment with the device exerts its effect early in the inflammatory phase of healing and promotes healing both in terms of time (observable based on the data obtained from the inflammatory infiltrate study) and quality, evident from the significant mast cell activation, resulting in greater histamine release, causing increased activation of various mediators and cell types that may be involved in the healing process.

IN-HUMAN ACUTE WOUND STUDY OBSERVATIONS AND ULCER CASE STUDY

The safety and efficacy clinical validation to obtain the CE marking for the EmoLED device for the treatment of acute surgical wounds is ongoing. **In particular, the acute observations, whose detailed results are provided in the attached final Report on the clinical trial, have once again demonstrated the device's safety and efficacy in shortening the healing time of spontaneously healing wounds.**

Isolated observations in patients with chronic lesions, of various aetiologies, have shown that the device is capable of unblocking the healing process, thus allowing the wound to progress beyond the inflammatory phase by inducing re-epithelialisation and wound closure. Observations made using a thermal camera have also shown that, due to the compromised condition of the tissues surrounding the ulcers, the baseline temperature of the limb is lower than normal and that both during and after treatment with the EmoLED device, the temperature never exceeds 40°C.

2. STUDY OBJECTIVES

The aim of this clinical study is to determine whether the proposed treatment represents a valid and significant treatment for ulcers by evaluating the percentage reduction of the area of the wound over a 10-week observation period and comparing the reduction of the area of the wound (or part of the wound), both on the same patient and within the entire group, treated with the EmoLED device, versus the control wound (or part of the wound) treated with a standard method. Over the 10-week period following their recruitment, the patients will continue to take their usual topical therapy and attend the weekly visits. Patients will be monitored:

- until healing, if this occurs before week 10,
- until week 10 in the event of incomplete healing.

Additionally, given that the device does not yet have CE marking, reports and assessments on the safety and usability of the device will be complied by the medical staff during the study.

3. ENROLMENT

A total of 90 subjects will be recruited by the facilities involved in this Clinical Study. Both hospitalised patients and outpatients receiving treatment will be considered for inclusion in this Study.

Patients will be assessed using a standard procedure that includes taking a medical history and a physical examination.

3.1 Inclusion criteria

- Subjects with venous, arterial or mixed skin ulcers and surgical wound dehiscence (18), (19);
- Presence of multiple similar wounds or one wound measuring² at least 5 cm;
- Men and women ≥ 18 years of age;
- Patients must be able to understand the aims of the Clinical Study and provide their informed consent in writing;
- Chronicity of the wound: at least 8 weeks.

3.2 Exclusion Criteria

The following will not be included in this study:

- Patients who participated in a clinical study on skin ulcer healing during the previous month;
- Patients who are unable to understand the aims and the objectives of the study;
- Patients with neoplastic ulcers;
- Patients with decubitus ulcers;
- Patients with diabetic foot ulcers;
- Patients with clearly infected ulcers;
- Patients with ulcers caused by critical ischaemia;
- Patients with a history of self-harm that can purposely alter the healing process;
- Patients with psychiatric disorders;
- Pregnant or breastfeeding women³;
- Patients with neoplasms or other diseases involving the use of cytostatic or immunosuppressive drugs;
- Patients with a short life expectancy.

In order for subjects to be eligible for inclusion in the treatment phase, all inclusion and exclusion criteria must be met before enrolment. Any concomitant drug therapies must be maintained.

3.3 Subject recruitment and screening

Enrollable patients will be selected by the Principal Investigator or his/her delegate based on the study inclusion and exclusion criteria. Once it has been verified that patients meet the study inclusion and exclusion criteria, the Principal Investigator or his/her delegate will ask the patients to consent to the use of the EmoLED device for treatment, after briefly explaining to them the key features of the device and the expected effect. If patients agree, they will enter the treatment phase. At the same time, patients will agree to return to the facility every week over the required observation period.

Patient registration in the identification register

Each trial site must keep a register of all subjects enrolled in the clinical trial and assign an identification code, an alternative subject identification or contact information. (UNI EN ISO 14155:2012 para. 6.5.2)

² In the event of multiple wounds, one wound will be treated with the EmoLED device and one will be chosen as the control wound; large wounds will be divided into two halves, one of which will be the control wound. This will reduce the variables associated with the inter-individual variability of skin lesions, thereby increasing the power of the test.

³ Pregnancy and breastfeeding will be verified based on the patients' declaration.

To comply with this specific requirement, the Principal Investigator will create, update and keep the Patient Identification Register.

The Patient Identification Register will contain the personal details of the patients who have given their consent to participate in the study, as well as the enrolment date and the patient code, comprising the acronym of the province of the facility followed by a three-digit sequential numerical code.

The patient code will be indicated in the Patient Case Report Form as Name (site ID code) and Surname (number) in order to create a database of photographic records.

Only the Principal Investigator and, at the discretion of the Principal Investigator, the members of his/her team will be aware of the identity of the patients enrolled in the study.

If a patient withdraws from the study, the Principal Investigator or one of his/her delegates will record the event in the Identification Register and on the Case Report Form and will archive everything.

Patient Enrolment Form

For each new patient, the Principal Investigator or his/her delegate will complete the Patient Enrolment Form with information such as patient identification (Name and Surname will be the same as in the Case Report Form, i.e., site ID code and number), age, gender, root cause of the ulcer, any concomitant conditions, any pharmacological therapies, date of onset of ulcers and recruitment date.

The second part of the form contains a table for recording the visit date, the patients' general health and the data collected at each visit.

Recording of clinical data

The data pertaining to the evaluation of the study endpoints will be acquired at specific time points as indicated in the Protocol and in the Study Case Report Form.

The parameters recorded on the Case Report Form will be acquired and maintained in paper format for the entire duration of the trial and stored both in paper and digital format, after scanning the Case Report Form, once a patient has completed the study; photographic images of wounds will be acquired, maintained and stored in digital format for the entire duration of the trial and afterwards.

The archiving code follows the patient recruitment code and the time of acquisition.

Case Report Form

The same Case Report Form will be used for all patients. It consists of many columns to be completed, one for each observation time point. At each observation time point, the doctor will mark the value chosen for each parameter with an "X" and the most appropriate description.

The Case Report Form will include a "Notes" section for recording additional information not initially envisaged that may be useful during the data analysis phase (e.g., patient's ethnic origin, special environmental conditions, patient's specific health conditions such as influenza or others, etc.).

Following the patient's completion of or withdrawal from the study, the Case Report Form will be scanned and archived.

Centralised database

The Principal Investigator of each site will send the Enrolment Form of any new recruited patients as well as the photographic records of the follow-up patients to the Project Manager on a weekly basis. The Case Report Forms of all patients who leave the study, whether healed or identified as drop-outs, will also be submitted.

Based on this data, the Project Manager will create a single database containing the data of all patients recruited, updated every week with the latest available data, accessible to the Principal Investigators. This database will allow the Investigators to monitor both the remaining number of patients yet to be recruited and the progress of the study.

4. STUDY DESIGN

4.1 General design

This clinical study will be a multicentre, prospective, controlled study, whose aim is to evaluate the clinical efficacy of a battery-powered portable device that uses blue LEDs.

As described in greater detail in the statistical analysis section, at least a 20% difference between treated and untreated wounds is expected to be observed in the same patient within the specified observation period.

For safety, the operator will be equipped with UV protection glasses. The housing of the device is made of biocompatible material that can be disinfected with detergents commonly used in hospitals in order to prevent contamination.

The device passed all safety tests (electrical, electromagnetic and photobiological) required by current regulations on medical devices, as well as a precise risk and usability analysis, and was found to be suited to the intended use.

The treatment, which is provided in addition to the patient's standard therapy, will be performed at each visit for 60 seconds on each 5-cm diameter sub-area of the selected wound or part of it.

Therefore, for multiple wounds, one will be treated with the EmoLED device and one will be selected as a control wound; very large wounds will be divided into two halves and one of the two will be the control wound. This will reduce any variability associated with randomised clinical trials (RCTs) on skin ulcer conditions.

4.1.1 Selection of the treatment area.

All wounds will be cleaned with saline solution and, if there is slough/black eschar, surgical debridement will be performed using a scalpel. Only at this point will treatment with the EmoLED device take place.

If a patient has more than one wound and all wounds at enrolment are found to have a **diameter of less than 5 cm**, the worst of the wounds will be treated entirely with the EmoLED device, whereas the others will serve as control wounds. Progression of all wounds will be evaluated over the ten-week study duration.

By contrast, if a wound at recruitment has a **diameter greater than 5 cm**, the wound will be divided into two halves along the longest side, and only one of the two halves will be treated. The other half of the wound will be dressed with a multi-layered sterile dressing. The division line between the two halves of the wound will be marked with a permanent marker, which will be reapplied at each visit, or whenever it begins to fade, to prevent loss of the reference marks.

If, at recruitment, a patient has more than one wound with a **diameter greater than 5 cm**, all wounds will be divided into two halves along the longest side and treated as described above.

After treatment with the EmoLED device, the wound will be dressed with a hydrofibre dressing. If clinical signs of infection occur, the wound will be dressed with a hydrofibre dressing with silver. The limb will then be bandaged with a compression bandage.

4.1.2 Standard treatment and data recording.

Any wounds or parts of wounds that are not treated with the EmoLED device will be medicated using the standard treatment consisting of a hydrofibre dressing or hydrofibre dressing with silver (as described above) and compression therapy. Ultimately, the treatment differs only for the fact that the EmoLED device is used in accordance with the procedure described above, while the rest of the treatment remains unchanged.

Following enrolment and the signing of the Informed Consent Form, the pertinent data from each patient will be recorded in the respective Case Report Form according to the following schedule: W0 (Week 0: enrolment and first treatment), W1, W2, W3 ... to W10, as per the routine visits over the 10-week period from enrolment.

Patients may miss a maximum of two non-consecutive follow-up visits over the 10-week period, starting from visit 5. Patients will be excluded from the study if consecutive visits are missed.

The parameters used to define the study outcomes will be based on:

- photographic images of the wounds treated with the EmoLED device as well as of control wounds
- Case Report Form completed by the doctor during the visits.

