6. STATISTICAL PLAN

Ninety subjects will be enrolled in this study. Each subject is part of both the control group and the treatment group.

Given that each patient will both receive the treatment and will also be a control subject, both groups will contain the same number of subjects, even if some of the subjects withdraw from the study. A comparative study of the subjects' demographic data and other baseline characteristics will also not be necessary as the two groups will be perfectly superimposable.

Treatment will be administered immediately after the cleaning and any necessary debridement of the complete wound. The area of the wound that should not be treated with the EmoLED device will be duly marked and covered with different layers of sterile dressing; this facilitates treatment standardisation and uniformity, thereby limiting any variability; it will also enable the treated, untreated and adjacent areas of each subject to be coherently defined.

The aim of the statistical analysis will be to establish the efficacy of the treatment with the EmoLED device; the significance ($p<0.05$) of any difference observed in the healing process between treated and untreated areas will be evaluated. Specifically, the primary endpoint of the study is the percentage reduction of the area of the wound treated with the EmoLED device versus the wound not treated with the EmoLED device at W10.

The secondary endpoints are:

1. Treatment safety.
2. Outcomes comparison in terms of the percentage reduction of the area of the wound treated with the EmoLED device versus the wound treated with SOC only within the ten-week observational period.
3. Evaluation of difference in healing time between the two areas.
4. Pain reduction (with pre-treatment assessment on a 0-10 VAS)
5. (OPTIONAL) Depending on the patient's willingness to continue to go to the study site, the observation of any unhealed area(s) over the 10-week period can be extended until complete healing or up to 20 weeks.

Estimation of sample size

The considerations underlying the choice of the model described below were drawn from a review of the literature on leg ulcer therapies and healing dynamics as well as on past clinical experience data obtained by the sites involved in the study with the treatment in question.

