The most significant finding yielded by the analysis of the clinical data in our possession is an expected 30% variability in the percentage reduction of the area of the wound at week 10. This value was confirmed by [15], where it was used to estimate the sample size. On the other hand, [16] found the standard deviation of the percentage reduction of the area of the wound to be 53% in the worst case and limited to venous ulcers only.

The analysis for the calculation of the sample size is based on:

- the clinical objective, which is represented by the percentage reduction of the area of the wound at W10
- a non-parametric statistical instrument for paired data, namely the Wilcoxon signed-rank test
- an a priori hypothesis of expected variability of 50% (conservative value)
- an expected 20% mean difference in the percentage reduction between the treated and the non-treated area
- a statistical power of 80% ($\beta=0.2$) and $\alpha=0.05$ will be considered
- a unilateral alternative hypothesis: the EmoLED treatment does not result in worsened outcome
- A correlation coefficient between percentage reductions of the treated and untreated area of 0.1, 0.3, 0.5 and 0.7
- A method for estimating the sample size based on asymptotic relative efficiency, compared to the t-test (minARE)

| | Estimate 1 | Estimate 2 | Estimate 3 | Estimate 4 |
|---|------------|------------|------------|------------|
| β | 0.2 | 0.2 | 0.2 | 0.2 |
| α | 0.05 | 0.05 | 0.05 | 0.05 |
| Diff. in % wound area reduction after 70 days | 20% | 20% | 20% | 20% |
| ρ | 0.1 | 0.3 | 0.5 | 0.7 |
| n | 83 | 65 | 47 | 29 |

The higher estimate is that relating to case 1, whose sample size is 83 subjects, which served as the basis for the choice of the number of subjects to be recruited, taking into account possible loss of subjects during treatment.

Statistical analysis of the primary endpoint.

A Wilcoxon signed-rank test with a significance level of 0.05 will be performed to evaluate the efficacy of use of the device. This test allows paired data to be handled and is robust enough to evaluate variability in observation distribution. A population analysis, as well as a per-protocol analysis (PP), will be performed for the subjects who complete the study.

Statistical analysis of secondary endpoints.

1. Treatment safety.

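### EmoLED is assigned by rule to an undefined worst wound, or to a half chosen by no stated rule, and never at random, so the unadjusted primary signed-rank test has no guaranteed null at zero

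*Combined protocol and SAP*

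**What the plan says.** Section 4.1.1 has two allocation rules.

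- **Several wounds, all under 5 cm:** "the worst of the wounds will be treated entirely with the EmoLED device, whereas the others will serve as control wounds". No criterion for *worst* is given.
- **A wound over 5 cm:** "the wound will be divided into two halves along the longest side, and only one of the two halves will be treated". Nothing says which half. The same applies when several wounds exceed 5 cm.

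Section 4.1 calls the study controlled, not randomised. Randomised trials appear only as a contrast to the paired layout: "This will reduce any variability associated with randomised clinical trials (RCTs) on skin ulcer conditions". The one safeguard on likeness within a pair is an inclusion criterion in section 3.1, "Presence of multiple similar wounds", and *similar* is not defined.

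For the primary endpoint, section 6 states: "A Wilcoxon signed-rank test with a significance level of 0.05 will be performed". No baseline covariate is named. The sample-size list gives "a unilateral alternative hypothesis"; the primary-analysis paragraph does not repeat the sidedness. On baseline data, section 6 states: "A comparative study of the subjects' demographic data and other baseline characteristics will also not be necessary as the two groups will be perfectly superimposable". No wound-level baseline table is planned, although section 4.1.2 bases outcomes on "photographic images of the wounds treated with the EmoLED device as well as of control wounds".

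**The concern.** A signed-rank test reads a shift from zero as a device effect. That needs paired differences symmetric about zero when the device does nothing. Random choice within the pair secures this by design. Giving the device to the worst wound ties treatment to wound state in every affected pair, and leaving the half open lets the operator choose.

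Pairing removes variation between patients. It does not remove a systematic difference between two wounds on the same patient. Percentage reduction scales each wound to its own starting area, which handles size only in part. It leaves depth, duration and tissue state alone and puts any W0 measurement error in the denominator.

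The sole primary comparison is at stake. A true benefit could be missed, or a difference could be credited to the device that belongs to the choice of wound.

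**Working it through.** **1. The plan's own sample size.** Inputs from section 6: SD 50 points, difference 20 points, one-sided alpha 0.05, power 80%, correlations 0.1 / 0.3 / 0.5 / 0.7, minimum-ARE method (efficiency factor taken as 0.864).

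SD of the paired difference = 50 × √(2(1 − ρ)) = 67.08 / 59.16 / 50.00 / 38.73. Paired-t power from the noncentral t with effective n = 0.864 N gives N = 83 / 65 / 47 / 29, exactly as printed. The two-sided version gives 105 / 82 / 60 / 37, so the printed figures are one-sided. The arithmetic is sound, but it takes a null centred at zero for granted.

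**2. What a shift does.** Let b be the difference in natural percentage reduction between the wound chosen for EmoLED and its control. The documents give no value for b. With n = 90 and ρ = 0.1:

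rejection rate ≈ Φ((effect + b) × √(0.955 n) / 67.08 − 1.645), where √(0.955 × 90) = 9.271.

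- Effect 20, b = 0: 20 × 9.271 / 67.08 − 1.645 = 1.119, about 87%.
- Effect 20, b = −3.9: 16.1 × 9.271 / 67.08 − 1.645 = 0.580, about 72%.
- Effect 0, b = +4: 4 × 9.271 / 67.08 − 1.645 = −1.092, about 14%.

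Simulated signed-rank tests (40,000 trials of 90 pairs, one-sided 5%) give, by share of pairs affected:

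| Case | All | Half | Quarter |
|---|---|---|---|
| Power for 20 points, b = −3.9 (86.4% at b = 0) | 71.2% | 79.8% | 83.2% |
| Power for 20 points, b = −8.2 | 48.8% | 70.3% | 79.1% |
| False positives, b = +4 | 13.6% | 8.3% | 6.5% |
| False positives, b = +1.2 | 7.0% | 5.9% | 5.4% |

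**3. Which shifts might arise.** All inputs here are assumptions. Take *worst* to mean larger area. Each wound's log area has SD s, and W0 area is measured with coefficient of variation c. The fraction remaining at W10 has mean m and rises by k per unit of log area, so larger wounds heal more slowly. If one W0 measurement both selects the wound and forms the endpoint's denominator, the net shift in points is:

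| k, m | s 0.2, c 0.10 | s 0.3, c 0.15 | s 0.3, c 0.20 | s 0.5, c 0.20 |
|---|---|---|---|---|
| 0.1, 0.55 | +0.7 | +1.1 | +4.0 | −0.7 |
| 0.1, 0.30 | −0.5 | −0.8 | +0.9 | −2.8 |
| 0.2, 0.55 | −1.3 | −2.0 | +1.1 | −6.1 |
| 0.2, 0.30 | −2.6 | −3.8 | −2.0 | −8.2 |

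Eleven of the 16 are negative, and four of the five positive ones are about +1. The last decimal depends on how measurement error is coded. The −8.2 end needs dissimilar wounds (median area ratio 1.6). Without that column the range is −3.8 to +4.0, with 7 of 12 negative. These are counts of assumed cases, not probabilities.

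If area is instead judged on a separate assessment with independent error of the same size, regression to the mean no longer enters the denominator selectively. All 16 shifts are then negative, from −2.0 to about −10.7.

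**4. The remedy.** Randomising within the pair centres the null at zero by construction, and the 83 pairs stand.

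**The case against.** **A reader might infer that the worst-wound rule inflates false positives in the device's favour.** The documents do not support that. Every positive shift above needs the same measured W0 area to select the wound and to form the denominator, and no section says *worst* is chosen that way. If *worst* means depth or tissue state, that mechanism need not arise. The 13.6% is one cell of 16 with every pair affected. If the primary test is two-sided, the favourable rate at +4 is about 8% against a nominal 2.5%.

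**A reader might equally infer that the rule is merely conservative.** That is not assured either. Slower healing of worse wounds costs power, the direction cannot be fixed from the documents, and the free choice of half can go either way.

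**The rule may reach few patients.** This stands as a limit. It applies only when all of several wounds are under 5 cm, and the share is not given. Halves of one wound share cause and patient, so the concern there is smaller. The similarity criterion also limits imbalance, although a rule that ranks one wound as worst presupposes some difference.

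**The baseline sentence may mean patient factors only.** It may, and then it is correct. It should not be read as a false claim about wounds. Wound-level balance is simply left unaddressed.

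**The study never claims to be randomised and prints its rule.** True, but printing the rule does not give the test a valid null.

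**Conclusion.** The point stands as a gap in allocation for the primary comparison, and it should be fixed before allocation begins. The plan gives no basis for a null at zero in separate-wound pairs, and none for split wounds beyond whatever the operator does in choosing the half.

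Confidence is high on the text and low on size. In separate-wound pairs, the more plausible result under the assumed models is a shift against the device: power for 20 points falls from about 86% to 71% at −3.9 if all pairs are affected, or 80% if half are. This uses SD 50, correlation 0.1, 90 pairs and one-sided 5%. The false-positive figures describe a conditional extreme, not an expected result. The grade rests on the missing allocation mechanism, not on these percentages.

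**What to change.** 1. **Randomise within a defined pair.** At W0, after debridement and marking, fix one index pair per patient by a stated rule (two wounds, or two halves of one wound). Randomise with concealment, for example sealed envelopes, which member gets EmoLED. To define the pair, first reconcile footnote 2 in section 3.3 and section 4.1 (one control wound) with section 4.1.1 (all the other wounds as controls, and several split wounds in one patient).
2. **Report at wound level.** Limit the comparability statement in section 6 to patient-level factors. Tabulate W0 area and wound duration for treated and control areas. Report split-wound and separate-wound pairs separately.
3. **If allocation has already been done,** apply step 2 and report the comparison as non-randomised. Any analysis adjusted for W0 area is supportive only: it does not address depth or tissue state, and where *worst* means larger area, treatment fixes the sign of the area difference, so precision is lost.

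**Cost.** A protocol amendment and an envelope system, with no extra patients or visits. W0 area is already needed for the endpoint. Date of onset is on the enrolment form but must be recorded per wound. The real downsides are that the worse wound will sometimes be the SOC-only control, and that the index-pair rule affects which wounds are studied.
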